6.6. Patient Disposition

Patient disposition will be displayed in a flowchart showing the number of patients entered, enrolled, randomized, and discontinued across all study periods.

Frequency counts and percentages of all randomized patients completing and discontinuing from the study and study treatment will be presented for each treatment group by period (0-26 Week, 0-52 Week, and 4-week safety follow-up period [Visit 801]). Reasons for discontinuation from the study and study treatment during the 26-week and 52-week treatment periods will be compared between treatment groups using Fisher's exact test. Reasons for discontinuation from the study at Visit 801 will be summarized by the randomized treatment groups.

At the primary objective database lock, a patient will be classified as a 26-week treatment completer if any of the following conditions holds:

- The patient has no study treatment discontinuation record whose visit number ≤ 18 ;
- The patient has a study treatment discontinuation record whose visit number = 18, and the number of days between the study treatment discontinuation date and the Visit 18 date is $< 10\%$ of expected number of days between Visit 17 and Visit 18 = $10\% * 28 \text{ days} = 3 \text{ day}$.

Frequency counts and percentages of all entered patients, enrolled, and discontinuing from the study during the lead-in period will be summarized. Reasons for discontinuation during screening will be summarized for all entered patients. Reasons for discontinuation from the study during the lead-in period will be summarized for all enrolled patients.

Time to all-cause discontinuation (discontinuation for any reason) from the study and from study treatment will be compared between treatment groups for the 26-week Treatment Period and the 52-week Treatment Period. The Kaplan-Meier product limit method will be used to create survival curves and the log-rank test will be used for the treatment comparisons. Time to all-cause discontinuation is defined as the total number of days between the randomization date (Visit 8 date) and date of discontinuation plus 1. Patients who complete the treatment period will be treated as censored using the total number of days between the randomization date and the Visit 18 (or Visit 22) date plus 1. If sufficient numbers of patients discontinue the study because of an AE, similar analysis will be performed for time to discontinuation due to an AE.

A listing of the primary reason for treatment discontinuation (if applicable) and study discontinuation will be generated for the Enrolled Population.

Patient allocation by investigator, grouped by country, will be summarized indicating the number of patients who enter the study, the number of patients who participate in the lead-in period, the

number of patients who are randomized to study treatment, and the number of patients who discontinue the study.

A listing of the randomization treatment assignment will be generated for all randomized patients.

6.7. Patient Characteristics

A summary table will be generated for patient characteristics at study entry using all randomized patients. The following variables will be included but not limited to: age, age groups (<40 and ≥40 years and 18 to 64, 65 to 85, and ≥85 years), sex, country, ethnicity, race, height, weight, body mass index (BMI), BMI groups (<25, ≥25 to <30, ≥30 kg/m²). For continuous variables, the following statistics will be provided: mean, SD, minimum, maximum, and median, and treatment groups will be compared using an ANOVA model with a term of treatment. For categorical variables, summary statistics will include sample size, frequency and percentage, and treatment groups will be compared using Fisher's exact test or Pearson's chi-square test. A listing of patient characteristics at study entry will be provided.

A similar summary of diabetes characteristics will also be generated. The following variables will be included but not limited to: duration of diabetes, the type of prandial insulin at study entry (that is, screening), the type of basal insulin therapy at study entry (including whether given once daily [QD] or twice-daily [BID]) and during lead-in, prandial insulin dosing plan, personal continuous glucose monitoring (CGM)/flash glucose monitoring (FGM) use during the study, HbA1c at study entry and baseline, HbA1c stratum at baseline, and fasting serum glucose at Visit 2 and baseline (based on MMTT).

A listing of patients whose stratification factor value entered into the IWRS (for treatment group assignment) is different from the clinical database will also be provided.

For all randomized patients, the number and percentage of patients with historical conditions will be summarized by treatment group using Medical Dictionary for Regulatory Activities (MedDRA) PT (without regard to SOC), and the number and percentage of patients with preexisting conditions will also be summarized by treatment group using MedDRA PT (without regard to SOC). Historical conditions are conditions that end prior to inform consent and preexisting conditions are conditions that are still ongoing at inform consent. Events will be ordered by decreasing frequency. No statistical comparisons between treatment groups will be performed.

6.8. Treatment Compliance

The prandial insulin dose times and meal times will be collected for assessing compliance of the timing of prandial insulin administration relative to meal time (premeal and postmeal). The difference between dose time and meal time will be calculated when both times are entered into the Electronic Clinical Outcomes Assessment (eCOA) device during the treatment period prior to discontinuation of IP for all randomized patients. Summary statistics will be presented for the difference between dose and meal times for each treatment group. The percentage of dose times within +/- 5 minutes of the protocol-specified dose timing (that is, -7 to +5 minutes for pre-meal

dosing and +15 to +25 minutes for postmeal dosing) will be summarized by treatment group. No statistical comparisons between treatment groups will be performed.

6.9. Important Protocol Deviations

Important protocol deviations (IPD) that potentially compromise the data integrity and patients' safety will be summarized by treatment group for all randomized patients. Patients with more than one IPD from the same category, subcategory, and study specific term (description) will only be counted once per patient.

Table 6.3 lists the categories/subcategories of important protocol deviations, source of identification, and the method to identify each deviation.

Table 6.3. Description of Important Protocol Deviations

Category	Sub-categories	Description	Source	Methods of Identification
Informed Consent	Informed Consent Not Obtained		Mixed (monitoring and clinical database)	Applicable to main protocol and CGM addendum. Compare all assessment dates to ICD date (except those assessments that may occur before ICD, eg, disease assessments).
Informed Consent	Improper Consent		Non Programmable (monitoring)	Applicable to main protocol and CGM addendum. Failure to re-consent after an ICD amendment at first possible visit. Unauthorized personnel administered ICD. Patient signed incorrect version of ICD (and failure to re-consent using the correct version of ICD prior to first CGM visit for the CGM addendum). ICD was not dated. ICD was lost.
Informed Consent	Revoke Consent		Non Programmable (monitoring)	Applicable to main protocol and CGM addendum. Patient revoked ICD.
Eligibility	Inclusion/Exclusion	Type of patient and disease characteristics	Mixed (monitoring and clinical database)	CRF Medical History, Diabetes Duration panel data to indicate diagnosis date of T1D per protocol <1 year prior to screening date, and Prior Diabetes Therapies / Basal Insulin / Bolus Insulin panel data to indicate start date for continuously using insulin <1 year prior to screening date. Also identified by CRA as captured in sCTMS. Entry Criteria #1.

Description of Important Protocol Deviations

Category	Sub-categories	Description	Source	Methods of Identification
Eligibility	Inclusion/ Exclusion	Age not in compliance with entry criteria	Mixed (monitoring and clinical database)	CRF data to indicate the age <18 yrs at Visit 1. Also identified by CRA as captured in sCTMS. Entry Criteria #2
Eligibility	Inclusion/ Exclusion	HbA1c not in compliance with entry criteria	Programmable (clinical database)	Central Laboratory data to indicate that entry HbA1c not compliant with entry criteria #5.
Eligibility	Inclusion/ Exclusion	Hematological conditions	Mixed (monitoring and clinical database)	CRF Pre-existing Conditions panel data using MedDRA terms that are considered as relevant hematological conditions by the CRP/CRS to indicate not compliant with entry criteria #25 Also identified by CRA as captured in sCTMS.
Eligibility	Inclusion/ Exclusion	Previous noninsulin antihyperglycemic medications	Mixed (monitoring and clinical database)	CRF Prior Diabetes Therapies / Concomitant Therapy panel data to indicate not compliant with entry criteria #32. Also identified by CRA as captured in sCTMS.
Eligibility	Inclusion/ Exclusion	Previous insulin therapy	Mixed (monitoring and clinical database)	CRF Prior Diabetes Therapies / Concomitant Therapy panel data to indicate not compliant with entry criteria #3, #4, #29, #30, #31. Also identified by CRA as captured in sCTMS.
Investigational Product	Treatment Assignment/ Randomization Error		Mixed (monitoring and clinical database)	IWRS data entry errors that impact patient stratification, for example, lab data indicated different strata from IWRS stratification report. Dispensing error: Patient was assigned to a treatment, but site gave a different treatment to the patient.
Investigational Product	Unblinding		Non Programmable (monitoring)	Any inadvertent unblinding affecting, patients, investigator, or sponsor.
Investigational Product	Patient Took Medication Not Fit for Use		Non Programmable (monitoring)	Study Drug not fit for use administered to patient.
Investigational Product	Other	Use of expired CT material	Non Programmable (monitoring)	Also identified by CRA as captured in sCTMS.

Description of Important Protocol Deviations

Category	Sub-categories	Description	Source	Methods of Identification
Study Procedures	Violation of Discontinuation Criteria		Mixed (monitoring and clinical database)	Patients not discontinued from treatment and/or study despite having met protocol specified discontinuation criteria. Also identified by CRA as captured in sCTMS Protocol Section 8.
Study Procedures	Excluded Conmeds		Mixed (monitoring and clinical database)	CRF Prior Diabetes Therapies / Concomitant Therapy panel data to indicate not compliant with entry criteria #28 and study-specific restriction on concomitant therapies Table ITRM.8 in the study protocol. Also identified by CRA as captured in sCTMS.
Study Procedures	Lab/Imaging Criteria	Missing HbA1c at baseline/at the primary endpoint	Mixed (monitoring and clinical database)	Central laboratory data to indicate that a). HbA1c is not collected at both Visit 7 and Visit 8 or b). HbA1c is not collected at the primary endpoint (only applicable to patients who completed the primary endpoint without early discontinuation from the study).
Study Procedures	Visit Schedule Criteria		Programmable (clinical database)	CRF Subject Visit panel data to indicate that 2 consecutive office visits are completely missing.
Study Procedures	Other	Electronic Clinical Outcomes Assessment (eCOA)	Programmable (clinical database)	Comparison of patient data from CRF and eCOA to identify randomized patients who have no ed diary data entered.
Administrative/Oversight	Suspected Misconduct		Non Programmable (monitoring)	Site staff sharing account details for systems (e IWRS, EDC or ePresentOnline). Suspected falsification of data.
Safety	Safety Mailings		Non Programmable (monitoring)	Lack of, significant delay in safety mailing review (significant delay defined as a delay of 90 days).
Safety	SAEs		Non Programmable (monitoring)	Failure to report an SAE within 24 hours of the investigator being made aware of the SAE. Failure to respond to SAE queries.

Description of Important Protocol Deviations

Category	Sub-categories	Description	Source	Methods of Identification
Safety	Other	Failure to report product complaint within 24 hours.	Non Programmable (monitoring)	Identified by CRA as captured in sCTMS.

Abbreviations: # = number of inclusion/exclusion criteria in protocols; CGM = continuous glucose monitoring; CRA = clinical research associate; CRF = clinical (case) report form; CRP = clinical research physician; CRS = clinical research scientist; CT = clinical trial; HbA1c = hemoglobin A1c; ICD = informed consent document; eCOA = Electronic Clinical Outcome Assessments; EDC = Electronic Data Capture; IWRS = interactive Web Response System; MedDRA = Medical Dictionary for Regulatory Activities; SAE = serious adverse event; sCTMS = Simplicity Clinical Trial Management System; T1D = type 1 diabetes; yrs = years.

Furthermore, of the above listed important protocol deviations, the following may significantly impact the results of the primary objective:

- lack of informed consent
- have any hematological condition that may interfere with HbA1c measurement
- missing HbA1c at both Visit 7 and Visit 8, or missing HbA1c at the primary endpoint.

Patients with one or more such deviations will be excluded from the Per Protocol (PP) population.

The listing of important protocol deviations for all randomized patients during the entire study, with the indication of whether to be excluded from the PP population, will also be provided. The IPDs identified by site monitoring and clinical database will be integrated in the listing. If an IPD is identified by both methods, only the site monitoring IPD will be presented.

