10.1. Sample Size Determination

Approximately 1199 patients will be randomized in order that 1020 patients complete the study through the primary endpoint at Week 26.

The primary objective of this study is to test the hypothesis that LY900014 is noninferior to insulin lispro on glycemic control as measured by change from baseline to Week 26 in HbA1c in patients with T1D when administered in a double-blind manner as prandial insulin (0-2 minutes before meals) in combination with basal insulin.

Patients will be randomized in a 4:4:3 ratio to double-blind LY900014 dosed 0 to 2 minutes before meals, double-blind insulin lispro dosed 0 to 2 minutes before meals, or open-label LY900014 dosed 20 minutes after the start of a meal (LY900014+20). Assuming a noninferiority margin (NIM) of 0.4%, no true difference between treatment arms, and an SD of 1.1%, approximately 371 completers in each double-blind treatment group will provide at least 99% power to show noninferiority between LY900014 and insulin lispro in change from baseline to 26 weeks in HbA1c using the upper limit of a 2-sided 95% confidence interval (CI) (LY900014 – insulin lispro). Assuming a 15% dropout rate for 26 weeks, approximately 1199 patients (436 in each double-blind treatment group and 327 in the open-label treatment group) will need to be randomized. This sample size also has 95% power to show noninferiority between LY900014 and insulin lispro using a 0.3% NIM at 26 weeks.

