10.3.2.4. Treatment Compliance

The proportions of patients compliant with timing of prandial insulin administration relative to meal time (premeal and postmeal) will be summarized.

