5.2. Determination of Sample Size

Assuming a noninferiority margin (NIM) of 0.4%, no true difference between treatment arms, and a standard deviation (SD) of 1.1%, approximately 371 completers in each double-blind treatment group will provide at least 99% power to show noninferiority between LY900014 and insulin lispro in change from baseline to 26 weeks in hemoglobin A1c (HbA1c) using the upper limit of a 2-sided 95% confidence interval (CI) (LY900014 – insulin lispro). Assuming a 15% dropout rate for 26 weeks, 4:4:3 randomization ratio (LY900014, insulin lispro, and LY900014+20), approximately 1199 patients will need to be randomized. This sample size also has 95% power to show noninferiority between LY900014 and insulin lispro using a 0.3% NIM at 26 weeks.

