6.11.3. Additional Analyses of the Primary Outcome

The primary MMRM analysis model will be repeated using the PP and Completer populations as a sensitivity analysis. If the conclusion differs from that of all randomized patients, the data and analyses will be further investigated.

A secondary analysis model for the efficacy estimand will be an ANCOVA for HbA1c change from baseline to the study primary endpoint, using the model with strata (pooled country, type of basal insulin, and prandial insulin dosing plan) and treatment as fixed effects and baseline as a covariate. Missing endpoints will be imputed using the LOCF approach using postbaseline data only.

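### The Per Protocol exclusions cover nothing about treatment received, so the Per Protocol set is close to the Completer set and is a weak check on dilution for the noninferiority claims

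*SAP*

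**What the plan says.** Both documents define PP as randomized patients who completed Week 26 without permanently stopping IP and without deviations serious enough to affect the primary objective. Patients are grouped by the treatment they actually received (Protocol 10.2; SAP Table 6.1).

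SAP 6.9 makes this operational. Table 6.3 lists the important deviations, among them "Dispensing error: Patient was assigned to a treatment, but site gave a different treatment to the patient", "Patients not discontinued from treatment and/or study despite having met protocol specified discontinuation criteria", inadvertent unblinding and excluded concomitant medication. The text then says "Furthermore, of the above listed important protocol deviations, the following may significantly impact the results of the primary objective" and names only lack of consent, a hematological condition that may interfere with HbA1c, and missing HbA1c (at both Visits 7 and 8, or at the primary endpoint). Only these lead to exclusion from PP.

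SAP 6.11.3 gives the set its role: "The primary MMRM analysis model will be repeated using the PP and Completer populations as a sensitivity analysis".

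Injection timing is not in Table 6.3. Protocol 10.3.2.4 says "The proportions of patients compliant with timing of prandial insulin administration relative to meal time (premeal and postmeal) will be summarized". SAP 6.8 plans summary statistics for the dose-to-meal interval and "The percentage of dose times within +/- 5 minutes of the protocol-specified dose timing", by treatment group.

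**The concern.** In a noninferiority comparison, patients who did not follow the regimen that defines their arm tend to make the arms look alike, and that favors the claim. A PP rerun is useful because it removes such patients and shows whether the conclusion survives. Here none of the three exclusions concerns which insulin was taken, what was taken with it, or whether treatment should already have been stopped.

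The result is an odd asymmetry. Protocol 8.1.1 requires IP to be stopped for prohibited medication, for unblinding of the patient, investigator or assessing staff, and after more than 14 consecutive days off IP. A patient handled that way leaves PP through the completion condition. A patient for whom the rule was broken has the worse deviation, yet counts as a completer and stays.

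Two claims depend on noninferiority: H1 (LY900014 against insulin lispro) and H5 (LY900014+20 against insulin lispro). H5 also acts as a gate. Under SAP 6.11.2 all alpha passes from H1 to H5 and only then to the other objectives. LY900014+20 is the same product at the same strength as mealtime LY900014, so adherence to injection time matters most for H5.

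**Working it through.** **What removes a patient from PP**

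| Situation | In Table 6.3 | Leaves by the completion condition | Leaves by the three exclusions |
|---|---|---|---|
| Complete swap of blinded insulin | yes | no | no, but analyzed under the insulin received |
| Both insulins used after a dispensing error | yes | no | no, and no grouping rule is given |
| Prohibited medication, IP stopped | yes | yes | not needed |
| Prohibited medication, IP continued | yes | no | no |
| Patient or site unblinded, IP stopped | yes | yes | not needed |
| Patient or site unblinded, IP continued | yes | no | no |
| More than 14 days off IP, then resumed | yes, as a missed discontinuation | no | no |
| Mistimed dosing | no | no | no |

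**How PP differs from Completer.** Apart from as-treated grouping, PP differs only by the three exclusions. A patient with no baseline HbA1c already drops out of the change-from-baseline model (SAP Table 6.2). An interfering hematological condition is already an entry exclusion (Protocol 6.2, criterion 25). That leaves consent failures, hematological conditions missed at entry, and completers without a Week 26 HbA1c. The documents give no counts, so the closeness of the two sets is inferred from the rules.

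**Inputs**
- SAP 5.2: "Assuming a noninferiority margin (NIM) of 0.4%, no true difference between treatment arms, and a standard deviation (SD) of 1.1" percent.
- Protocol 10.1: "approximately 371 completers in each double-blind treatment group will provide at least 99% power".
- Protocol 10.1: 327 patients randomized to LY900014+20 with 15% dropout, so 327 × 0.85 = 278 completers.
- Two-sided 95% confidence interval, so z = 1.96.
- f, the share of the comparison that shows no treatment difference: assumed, 2% to 20%.

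**The plan's own figures reproduce**
- SE(H1) = 1.1 × √(2/371) = 0.0808.
- Power at 0.4%: Φ(0.4/0.0808 − 1.96) = Φ(2.99) = 99.9%, stated as at least 99%.
- Power at 0.3%: Φ(0.3/0.0808 − 1.96) = Φ(1.75) = 96.0%, stated as 95%.

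The sample size is not in dispute.

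**Illustration for H5**

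SE(H5) = 1.1 × √(1/371 + 1/278) = 0.0873. If the true difference equals the margin and a share f shows none, the expected difference is 0.4(1 − f). False noninferiority is then Φ(0.4f/0.0873 − 1.96).

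| f | Expected difference | False noninferiority |
|---|---|---|
| 0 | 0.400 | 2.5% |
| 2% | 0.392 | 3.1% |
| 5% | 0.380 | 4.2% |
| 10% | 0.360 | 6.7% |
| 20% | 0.320 | 14.8% |

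**Cost of a stricter set** (power at the 0.4% margin, no true difference, same share removed from both arms)
- H1, 10% removed (333 per arm): Φ(0.4/0.0852 − 1.96) = 99.7%.
- H1, 20% removed (296 per arm): Φ(0.4/0.0904 − 1.96) = 99.3%.
- H5, 10% removed (333 and 250): SE = 0.0921, power 99.1%.
- H5, 20% removed (296 and 222): SE = 0.0977, power 98.4%.

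**The case against.** The strongest reply is that PP decides nothing. Noninferiority is declared from the ITT ANCOVA and the efficacy-estimand MMRM on randomized patients (SAP 6.11.1), and a different PP set leaves the error rate of those tests unchanged. This stands. A reader might take the percentages above as the trial's false-positive rate; they are not.

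Part of the dilution is also handled already. As-treated grouping deals with a complete swap. Patients stopped as Protocol 8.1.1 requires leave PP, and the MMRM uses on-IP data. Sites confirm each pen number in the interactive web-response system (Protocol 7.2). Deviations are summarized by arm and listed with PP status, and concomitant medication is compared between arms. A reader might infer that all wrong-insulin and prohibited-drug patients remain, or that the PP rerun cannot detect dilution. Neither follows. What remains is mixed exposure and patients wrongly kept on IP.

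A reader might extend the timing argument to H1. Both H1 arms inject 0 to 2 minutes before the meal, so mistiming is not cross-over there and the direction of any bias is not established. Nor do the documents show that deviations in screening HbA1c or prior therapy pull the difference toward zero: all patients use lispro for an 8-week lead-in, and baseline HbA1c is in the model.

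Finally, excluding patients on post-randomization adherence can itself introduce bias. Dose and meal times are collected mainly for 3 days before visits and on 10-point profile days (Protocol 9.1.4.1), so a timing cutoff would classify patients from a sample of doses. This is a sound reason to keep timing out of the PP definition. It does not bear on the treatment-related flags, which SAP Table 6.3 already treats as important.

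**Conclusion.** The point holds as a weakness of a sensitivity analysis. The PP exclusions contain nothing about treatment received. Patients with mixed insulin exposure, and those left on IP despite prohibited medication, unblinding or more than 14 days off IP, stay in. The two planned reruns therefore largely repeat each other, and PP is a weak check on dilution. Protocol 8.1.1, had it been followed, would have removed the second group; no stated rule removes the first.

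The size cannot be fixed from the documents because no deviation rate is given. For H5 the illustration is minor at 2% and becomes material at roughly 5% to 10%. It assumes a true difference equal to the margin, no effect at all in the retained deviators, and the planning SD and completer numbers. It describes any analysis that keeps such patients.

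Separately, the protocol promises the proportion of patients compliant with timing, whereas the SAP reports a proportion of doses. SAP 6.11.3 also does not say whether H5 is read from the PP model, although that model contains all three arms.

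**What to change.** Before unblinding, amend the SAP as follows.

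1. In 6.9, add to the PP exclusions the existing Table 6.3 flags for:
   - dispensing error with any use of another arm's IP;
   - excluded concomitant medication that affects glycemia;
   - unblinding of the patient or site;
   - violation of discontinuation criteria, where the criterion bears on HbA1c or on treatment received.

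   Where one of these is left out, give the reason.
2. In 6.11.3, state that the H1 and H5 contrasts are both read from the PP MMRM.
3. In 6.8, report the patient-level proportion compliant with dose timing that Protocol 10.3.2.4 promises, with the definition of a compliant patient fixed in advance. Use it in a supportive analysis of H5, outside the PP definition.

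No eligibility exclusions and no timing cutoff for PP membership are needed.

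The cost is SAP wording, programming of flags and times already collected, and a slightly smaller PP set. At the 0.4% margin, power stays at 98% or more for both contrasts even with 20% removed.
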